8.1 Participant Withdrawal

While participants are encouraged to complete all study evaluations, they may withdraw from the study at any time and for any reason. Participation is voluntary, and refusal to participate will involve no penalty, or loss of benefits to which the participant is otherwise entitled. The participant will be encouraged to maintain contact with the investigator and report any serious adverse events experienced for the 6 months study period. Follow-up following the study period is described in Section 7.13.

An **evaluable** participant will be any participant who receives at least one dose of test material and has at least one post dose assessment.

Screen failures will include any participant who consented and entered into the screening process appropriately, but subsequently did not meet the entry criteria and was not administered study drug. Participants who fail screening will not be followed for safety or activity of study drug, and no other study procedures will be performed.

Up to a maximum of 3 participants per dose group may be replaced if participants drop out prior to completion of week 4 post study drug.

8.2 List of withdrawal criteria

WITHDRAWAL OF A PARTICIPANT DUE TO ANY SERIOUS ADVERSE EVENT REQUIRES THAT THE SPONSOR BE INFORMED **WITHIN ONE WORKING DAY AFTER THE INVESTIGATOR IS MADE AWARE OF THE EVENT.** PLEASE REFER TO SECTION 9, ADVERSE EVENT REPORTING.

Those participants who do not complete the study for any reason will be considered a premature termination. The procedures for the Visit 8 should be completed when a participant discontinues the study.

- **Adverse Events:**

Participants with adverse events, severe enough to necessitate discontinuation of study drug administration as judged by the investigator.

The treating physician should take appropriate clinical action. The condition should be treated according to routines of the clinic. The participant should be followed up regarding the safety measurements stated in the protocol.

- **Consent Withdrawn:** participant decided to withdraw from the study for non-medical reasons that the investigator/patient deemed sufficient to warrant premature termination.
- **Lost to Follow-up:** participant failed to return for required visits and cannot be contacted. Reasonable effort should be made by the investigator to contact any patient who fails to return to the clinic for a scheduled visit in order to complete assessments and retrieve any outstanding data. All such efforts should be documented in the source notes.
- **Sponsor/Investigator Decision:** A participant may be withdrawn at any time at the discretion of the investigator.

If a participant discontinues from the study, she should always be contacted in order to give the investigator information about the reason(s) for discontinuation and any adverse events. Whenever possible, the patient should return for a clinic visit at the time of or soon after discontinuation. Any outstanding data or study medication should be collected. Adverse events should be followed up.

8.3 Reasons for withdrawal

The participants may withdraw from the study if they decide to do so, at any time and irrespective of the reason, or at the Investigator's decision. Participants who have been withdrawn from the study cannot be re-included in the study. Their inclusion and treatment number must not be re-used.

8.4 Replacement of participants

Up to 3 replacements per dose will be allowed for participants who received study drug and discontinued without follow-up data of at least one-month post study drug administration.

8.5 Withdrawal follow-up procedure

For participants considered lost to follow-up, the E-CRF must be filled in up to the last visit.

9.1 Adverse Events Definitions and Monitoring

9.2 Adverse Event

An adverse event is any unfavorable and unintended diagnosis, symptom, sign (including an abnormal laboratory finding), syndrome or disease which either occurs during the study, having been absent at baseline, or, if present at baseline, appears to worsen.

9.3 Serious Adverse Event

A serious adverse event (experience) is defined (21 CFR 312.32) as any adverse experience that suggests a significant hazard, contraindication, side effect, or untoward medical occurrence that:

- Results in death,
- Is life threatening,

Note: The term "life-threatening" in the definition of "serious" refers to an event in which the participant was at risk of death at the time of the event; it does not refer to an event which hypothetically might have caused death if it were more severe.

- Requires (or prolongs) hospitalization, including emergency room care,
- Causes persistent or significant disability/incapacity,
- Results in congenital anomalies or birth defects, or
- Other conditions which in the judgment of the investigators represent significant hazards.

Medical and scientific judgment should be exercised in deciding whether expedited reporting is appropriate in other situations, such as important medical events that may not be immediately life-threatening or result in death or hospitalization but may jeopardize the participant or may require intervention to prevent one of the other outcomes listed in the definition above.

These should also usually be considered serious.

Note: Examples of such events are intensive treatment in an emergency room or at home for allergic bronchospasm, blood dyscrasias, convulsions or asymptomatic ALT increase > 10 ULN that do not result in hospitalization, or development of drug dependency or drug abuse.

9.4 Assessment of Causality

The relatedness of an adverse event to the study drug is the best estimate of the principal investigator at the time of reporting of the causal relationship between an experimental intervention and an adverse event.

The following study drug relationships will be used for this clinical trial:

Unrelated: There is no temporal relationship between the event and the administration of the study drug or the event is clearly due to the participant's medical condition, other therapies, or accident.

Possibly Related: There is some temporal relationship between the event and the administration of the study drug and the event is unlikely to be explained by the participant’s medical condition or other therapies.

Probably Related: The temporal relationship between the event and the administration of the study drug is compelling, and the participant’s medical condition or other therapies cannot explain the event.

Definitely Related: The event follows a reasonable temporal sequence from administration of the medication or follows a known or suspected response pattern to the medication.

The categories of “Certainly”, “Probably” and “Possibly Related” are considered study drug related.

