Study Objectives The primary objective of this study is to evaluate occurrence of Adverse Events and their relationship to *hMaxi-K* following multiple intramuscular (IM) injections into the bladder wall. Two dose levels (16000 µg and 24000 µg by IM injection into the bladder wall) in females with moderate OAB/DO of \geq six months duration are initially planned. **Pending safety and efficacy results for the 2 doses that are planned, the protocol may be amended to investigate additional doses in this study.**

The secondary objectives of this study are to evaluate the following safety parameters:

- Clinical laboratory tests- changes from baseline
- Electrocardiogram change from baseline
- Physical Examination- changes from baseline

These changes will be evaluated primarily at the individual level, through clinical assessment of outliers supported by descriptive statistics. In addition efficacy parameters will be evaluated (change from baseline compared to placebo), including number of micturitions per day, volume per micturition, incontinence episodes, pad weight, uninhibited contractions during cystoscopy, and general and bladder specific quality of life assessments.

Study Design This study is a double blind, placebo-controlled, multicenter, sequential active dose, phase 1 study in females with moderate OAB/DO of \geq six months duration. The proposed study period is approximately 6 months following a single administration of study drug by multiple IM injections into the bladder wall per participant. The protocol sample size of this phase I study is not intended to support the statistical significance of the primary endpoint as outlined in the study objectives. Rather, the sample size takes into account clinical safety considerations. Nine participants per dose level are planned: [6 assigned active treatment and 3 assigned placebo (PBS-20% sucrose only control group)]. Therefore a total of up to 9 participants will be enrolled in each dose group. Each arm of participants will be enrolled sequentially and enrollment into the next higher dose level will be dependent on assessment of safety. The participants chosen will be assigned in a

**Study
Population**

randomized fashion to either placebo or an active treatment group within each group.

The study population is women ≥ 18 years old of non-child bearing potential¹ with overactive bladder (OAB) and detrusor overactivity who are otherwise in good health.

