10.1. Adverse Events

Safety summaries will include the incidence of treatment-emergent adverse events (TEAEs), which are defined as any event that began on or after the date of the first treatment dose or worsened in severity or frequency after treatment dose was initiated. Events worsening in severity will be considered new AEs. AEs recorded on the CRF that began prior to treatment and did not worsen in severity will be recorded as medical history will not be included in the AE summary tables and data listings. Any AEs happens in long-term safety follow-up will be reported in a separate listings and not included in the main planned analyses.

All TEAEs will be coded using version 17.1 of Medical Dictionary for Regulatory Activities (MedDRA) and summaries will present data by System Organ Class (SOC) and preferred term (PT).

The following conventions will be followed in summarizing multiple occurrences of an adverse event for a certain assessment period when summarizing data from individual participant:

- Each subject will be counted only once within a body system (SOC) or a preferred term;
- The highest known severity within a body system or a preferred term will be assigned to the event;
- The strongest relationship within a body system or a preferred term will be assigned to the event.

The denominator used for calculation of the percentages will be the number of subjects in the Safety population per treatment.

Specifically, TEAEs will be summarized in the Safety Population. An overall summary of TEAEs, including number of subjects in population, number of subjects with one or more TEAEs, number of participants with one or more Serious TEAEs, number of deaths (if any), and number of subjects experiencing AEs resulting in discontinuation, will be presented in Table 14.3.1.1 by treatment group. The frequency and percentage of AEs by SOC and PT for each treatment group will be presented in Table 14.3.1.2.

The frequency and percentage of AEs related to study drug (Possibly Related, Probably Related, and Definitely Related) by treatment group will be displayed by treatment in Table 14.3.2.

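### Protocol 9.4's causality scale is neither ordered nor mutually exclusive: *Definitely Related* sets no condition on other causes, so the relatedness of TEAEs may be unreliable

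*Protocol*

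**What the plan says.** Protocol 9.4 makes causality the principal investigator's best estimate and defines four categories:

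- *Unrelated* requires this: "There is no temporal relationship between the event and the administration of the study drug or the event is clearly due to the" … (illness, other treatment or an accident).
- *Possibly Related* requires this: "There is some temporal relationship between the event and the administration of the study drug and the event is unlikely to be explained by" … (illness or other treatment).
- *Probably Related* requires this: "The temporal relationship between the event and the administration of the study drug is compelling, and the" … (illness or other treatment cannot account for it).
- *Definitely Related* requires this: "The event follows a reasonable temporal sequence from administration of the medication or follows a known or suspected response pattern to the medication".

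Section 9.4 closes by stating that Certainly, Probably and Possibly Related "are considered study drug related". No category called Certainly is defined; SAP 10.1 uses Definitely. Protocol 9.6 asks separately for the investigator's opinion on whether there is a reasonable possibility that the drug caused the event, and does not tie the answer to the four categories.

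On use, the Protocol Synopsis says: "The primary objective of this study is to evaluate occurrence of Adverse Events and their relationship to" hMaxi-K. Under that objective the SAP Synopsis lists TEAEs by relationship to study drug. SAP 10.1 puts *Possibly*, *Probably* and *Definitely* into Table 14.3.2 as related events. Where a participant has several events, "The strongest relationship within a body system or a preferred term will be assigned to the event".

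**The concern.** A causality scale should ask for more evidence at each step up, and each event should land in one place. Here the condition on other causes tightens from *Possibly* to *Probably* and then disappears at *Definitely*. An event with suggestive timing and a credible other cause is weak evidence against the drug, yet the literal text can send it to the strongest label.

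Relationship to treatment is one of the two parts of the primary objective. A rule that keeps the strongest relationship presupposes an ordered scale: without one, a single event graded *Definitely* on timing alone sets that participant's entry for the whole preferred term or body system. With up to six sites, investigators must either follow the text and give odd labels, or apply their own unstated rules, which may differ.

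**Working it through.** The plan states no figure to reproduce. The check is whether the four definitions sort events.

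**Step 1. Conditions side by side (Protocol 9.4).**

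| Category | Timing | Other causes | Known response pattern |
|---|---|---|---|
| *Unrelated* | none, **or** → | clearly due to one | not used |
| *Possibly* | some, **and** → | unlikely | not used |
| *Probably* | compelling, **and** → | cannot explain | not used |
| *Definitely* | reasonable, **or** pattern | no condition | suffices by itself |

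**Step 2. Enumerate event profiles.** Assumed levels, taken from the wording: timing (none, some, reasonable, compelling) × other cause (clearly due, plausible, unlikely, cannot explain) × known pattern (no, yes) = 4 × 4 × 2 = 32 profiles. The text does not say whether *some* timing is weaker than *reasonable*, so both readings were run. Stronger timing is taken to satisfy a weaker timing condition.

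| Result | *some* weaker than *reasonable* | *some* = *reasonable* |
|---|---|---|
| Fits no category | 1 | 0 |
| Fits exactly one | 12 | 10 |
| Fits two or more | 19 | 22 |
| Fits both *Unrelated* and *Definitely* | 9 | 10 |
| *Possibly* profiles that also meet *Definitely* | 10 of 12 | 12 of 12 |
| *Probably* profiles that also meet *Definitely* | 2 of 2 | 2 of 2 |
| Plausible other cause, fits *Definitely* only | 5 | 6 |

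Under the first reading, the 9 overlaps with *Unrelated* are: no timing but a known pattern, 4; clearly due to another cause with reasonable or compelling timing, 2 × 2 = 4; clearly due to another cause with some timing and a known pattern, 1. The one profile with no category has some timing, a plausible other cause and no known pattern.

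If an investigator gives each event the highest category it meets, *Probably* is never used under either reading. *Possibly* survives for 12 − 10 = 2 profiles under the first reading and 12 − 12 = 0 under the second.

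**Step 3. Which outputs move.** *Possibly*, *Probably* and *Definitely* all count as related, so disorder among them changes the graded summary but not the pooled related count. That count can change where an event meets both *Unrelated* and *Definitely*. Group sizes come from SAP 3.2, and each participant is counted once per preferred term or body system:

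- one dose arm, or the combined placebo group: 1/6 = 16.7 percentage points;
- pooled active group: 1/12 = 8.3 percentage points.

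This is the size of one crossing. It requires that the participant has no other related event in that row of the table.

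**The case against.** Several points on the other side are fair.

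- **Judgement.** Causality is the investigator's best estimate, so the literal text need not be applied mechanically. This stands as a reason to speak of risk and not of an observed error. It does not make the definitions usable or consistent between sites.
- **Blinding.** Placebo is given by the same injections under double blinding, so misuse should fall on both groups in a similar way. This limits bias in the comparison, but it does not make either group's graded labels reliable.
- **Listing.** SAP 10.1 lists all adverse event data by participant, so grades can be re-examined. That is a later repair and would itself need a defined scale.
- **Certainly.** This is a label slip. The SAP names the three related categories correctly and no count changes.

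A reader might infer more than the documents support:

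- **That every early event with another possible cause shifts the related rate by 17 points.** A urinary tract infection after catheterisation shows otherwise. Treating catheterisation as another cause, the infection is *Definitely* under the literal text and *Possibly* under a corrected scale. Both count as related, so the shift is 0. The earlier OAB trial does not help: it reports one such infection as possibly related and the others as unrelated, without onset times or the causality scale used.
- **That the scale leaves a gap.** This holds for 1 profile of 32, and only if *some* is weaker than *reasonable*. Otherwise that event falls into *Definitely*, which is an ordering fault.
- **That the procedure is plainly another cause.** Protocol 2.1 and SAP 3.1 describe the treatment as the 20 to 30 injections, so whether procedural events count as treatment related is a substantive choice.

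**Conclusion.** The scale in Protocol 9.4 is not ordered and not mutually exclusive, under both readings of *some* timing. The graded relationship of TEAEs and the strongest-relationship rule may therefore be unreliable. The related count in Table 14.3.2 can change for events that meet both *Unrelated* and *Definitely*, by 16.7 points per participant in an arm of 6 and 8.3 points in the pooled active group of 12.

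It would go too far to say that the primary safety outcome is misclassified. TEAE incidence, the body system and preferred term table, severity, SAEs, deaths and discontinuations do not use these categories, and neither do the stopping rules in Protocol 5.2.1. The documents show a risk to the relationship part of the objective, not that misclassification occurred. The profile counts rest on the assumed levels and on literal reading; they show how often the definitions collide, not how often real events would. The wording should be corrected because a rule that gives the wrong label when followed feeds a primary objective.

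**What to change.** Rewrite Protocol 9.4 as an ordered, mutually exclusive scale:

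- *Unrelated*: no temporal relationship, or clearly due to another cause.
- *Possibly*: temporal relationship, but other causes could also explain the event.
- *Probably*: temporal relationship, and other causes unlikely.
- *Definitely*: reasonable temporal sequence **and** known or suspected response pattern **and** no other explanation.

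State that *Unrelated* is decided first, and that otherwise the highest level whose conditions are all met is assigned. On the 32 profiles this gives 14 *Unrelated*, 6 *Possibly*, 10 *Probably* and 2 *Definitely* (14 + 6 + 10 + 2 = 32), one category each. If *some* equals *reasonable*, it gives 14 + 6 + 9 + 3 = 32.

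In addition:

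- replace Certainly with Definitely in the closing sentence of 9.4;
- map the reasonable-possibility opinion in Protocol 9.6 to the scale;
- have the sponsor state whether events due to the injection procedure count as related to study treatment.

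The cost is protocol wording and eCRF completion guidance. No extra data are needed.

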9.5 Severity of Adverse Event

Adverse events included in the toxicity table (Appendix A) will be graded according to the definitions provided. For adverse events not listed in the toxicity table, assignment of grade based on intensity of symptoms, degree of limitation of usual daily activities, or level of abnormality of objective clinical signs or laboratory parameters will be according to severity using the following criteria:

- Grade 1: transient or minimal symptoms; not interfering in function or ability to perform activity of daily living or require a medication change. No medical intervention required.
- Grade 2: symptoms interfering in function but not with activities of daily living. Minimal or no medical intervention required.
- Grade 3: incapacitating symptoms that interfere with function and activities of daily living; required bed rest and/or resulted in loss of work or cancellation of social activities. Medical intervention required. Hospitalization possible.
- Grade 4: Medical intervention is required to prevent permanent impairment or death; OR Permanently Disabling: bed-ridden or disabling, significant medical intervention/therapy required, hospitalization or hospice care possible.

9.6 Monitoring of Adverse Events

The investigator will monitor participants for the occurrence of adverse events during the course of the study and record all observed adverse events in the electronic case report form.

All Adverse Events regardless of seriousness or relationship to study drug, including those occurring during the Screening period (where applicable), are to be recorded on the corresponding page(s) in the E-CRF. Whenever possible, symptoms should be grouped as a single syndrome or diagnosis. The Investigator should specify the date of onset, maximal intensity, corrective therapy given, outcome, and his/her opinion as to whether there is a reasonable possibility that the Adverse Event was caused by the study drug.

The investigator must provide the sponsor appropriate information concerning any findings suggesting significant hazards, contraindications, side effects or precautions pertinent to the safety of the study drug. The investigator will instruct participants prior to administration of study drug to report any physical changes or new symptoms that they notice during the course of the study. The investigator must report all serious adverse events (defined above) within 24 hours of their onset or following the investigators awareness of the event to the Sponsor's designee:

[name]
[contact]
[contact]
[contact]

Or

[name]
[contact]
[contact]

The Sponsor or designee will report all serious adverse events to the IRB, FDA, OBA, and NIH according to regulatory requirements. Any adverse event that is not resolved by the end of study (or early termination) visit and considered to be potentially related to study drug, or was the cause for participant withdrawal will be followed as clinically indicated until its resolution, or if non-resolving, until considered stable.

In the case of a Serious Adverse Event the Investigator must immediately:

- SEND (within 1 working day if possible) the signed and dated corresponding page(s) in the SAE Report Form to the Sponsor (as above) or designee. The date of receipt of this form by the Sponsor will be the date used as "Day 1" for expedited reporting to the regulatory agencies as is required.
- ATTACH the photocopy of all examinations carried out and the dates on which these examinations were performed. For laboratory results, include the laboratory normal ranges.
- All additional data or corrections are to be reported on a follow-up SAE form.
- A blinded code must be broken only in exceptional circumstances when knowledge of the study medication is essential for treating the participant.

Follow-up Procedures

- The Investigator should take all appropriate measures to ensure the safety of the participants, notably he/she should follow-up the outcome of any Adverse Events (clinical signs, laboratory values or other, etc.) until the return to normal or until stabilization of the participant condition.
- In the case of any Serious Adverse Event, the participant must be followed up until clinical recovery is complete and laboratory results have returned to normal, or until progression has been stabilized.
- In case of any Serious Adverse Event brought to attention of the Sponsor.

ECG Monitoring

In case of prolongation of $QT_cF \geq 500$ ms, or an increase in $QT_cF \geq 60$ ms from baseline, a blood sample should be drawn for potassium, calcium, magnesium and a plasma assay for *hSlo* cDNA with PCR. The *hSlo* analysis will be done by the under the direction of [name]. of the Department of Urology Research Laboratory, Albert Einstein College of Medicine.

A cardiologist should be consulted, and the participant should continue to have his or her ECG monitored until the ECG abnormality resolves or becomes stable and part of the patient's new medical history.

